In G1T28-02, a total of 19 patients were treated in the dose exploration Part 1, and 75 patients were treated in the placebo-controlled, double-blinded, randomized Part 2. (Please see the current version of the trilaciclib IB for detailed information on Part 1 patients.) The unblinded randomized results from Part 2 provide proof-of-concept evidence of the myelopreservation benefits of trilaciclib combined with E/P compared with placebo + E/P. The trilaciclib arm was favored across all neutrophil-related endpoints, including the proportion of patients with Grade 4 absolute neutrophil count (ANC) values (16/37 [43.2%] for placebo versus 2/38 [5.3%] for trilaciclib: p-value = 0.0001) and dose reductions due to neutropenia (10/37 [32.4%] for placebo versus 2/38 [5.3%] for trilaciclib: p-value = 0.0033). In alignment with the reduction of Grade 4 ANC events, the proportion of patients who received granulocyte colony-stimulating factor (G-CSF) was also significantly lower in the trilaciclib group (4/38 [10.5%]) than in the placebo group (24/37 [64.9%]: p-value < 0.0001). RBC endpoints also favored trilaciclib versus placebo, eg, 2/35 (5.7%) of patients enrolled on the trilaciclib arm received an RBC transfusion on/after Week 5 versus 8/37 (21.6%) of patients in the placebo arm. In addition, mean lymphocyte counts over time in the trilaciclib arm were greater than those observed in the placebo arm, and the recovery to baseline after each chemotherapy-induced lymphocyte nadir was faster in the trilaciclib arm compared with the placebo arm. Consistent with the faster recovery of lymphocyte counts, E/P + trilaciclib, as compared to E/P + placebo, not only increased the total number of circulating CD8+ cells during treatment, but also resulted in a larger population of activated CD8+ T cells, and fewer regulatory T cells; both of which are consistent with a more robust immune response which could correlate with improved antitumor responses. In Part 2, almost all patients reported at least 1 TEAE, and almost all patients reported TEAEs related to etoposide or carboplatin. Approximately half the patients reported TEAEs related to trilaciclib, but none were  $\geq$  Grade 3, which suggests that trilaciclib is not associated with severe toxicity. There were notably fewer high-grade ( $\geq$  Grade 3 and  $\geq$  Grade 4) TEAEs reported during treatment with trilaciclib compared with placebo, an observation primarily driven by a significant decrease in the number of hematologic high-grade TEAEs reported in the trilaciclib arm. Fatigue, nausea, thrombocytopenia, and anemia were the most frequent TEAEs in the trilaciclib group. Neutropenia, anemia, alopecia, and thrombocytopenia were the most frequent TEAEs in the placebo group.

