**Table 8-3 Etoposide and Carboplatin Dose Adjustments Based on Absolute Neutrophil Count Nadir With or Without Fever**

ANC Nadir	Etoposide	Carboplatin
Grade 3a (without fever)	No Change	No change
Grade 4b for ≥ 7 days (without fever)		
First episode	No change. Use G-CSF with subsequent cycles. Refer to the ASCO guidelines (Smith 2015).	No change. Use G-CSF with subsequent cycles. Refer to ASCO guidelines (Smith 2015).
Second episode	First dose reduction	First dose reduction
Third episode	Second dose reduction	Second dose reduction
Fourth episode	Discontinue drug	Discontinue drug
Grade 3/4 with fever		
First episode	No change. Use G-CSF with subsequent cycles. Refer to the ASCO guidelines (Smith 2015).	No change. Use G-CSF with subsequent cycles. Refer to ASCO guidelines (Smith 2015).
Second episode	First dose reduction	First dose reduction
Third episode	Second dose reduction	Second dose reduction
Fourth episode	Discontinue drug	Discontinue drug

ANC = absolute neutrophil count; G-CSF = granulocyte colony-stimulating factor

a Grade 3 ANC: 500 to < 1000/mm^3

b Grade 4 ANC: < 500/mm^3

Platelets

The dose adjustments in [Table 8-4](#) are based on the platelet nadir during the preceding treatment cycle.

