## 8.6. Prior and Concomitant Medications and Procedures

All concomitant medications including prescription medications, over-the-counter preparations, growth factors, blood products, and parenteral nutrition taken during the 14 days before the date of enrollment, during the study treatment, and through 30 days after the last dose of study drug will be documented. Documentation will include information regarding start and stop dates, dose(s), and reasons for the medication use.

Administration of other concomitant nonprotocol anticancer therapies prior to progression is not permitted while on this study.

Administration of other concomitant investigational agents for any indication is not permitted while on this study.

Palliative radiation therapy or surgery is allowed to control disease symptoms but not to aid in the response of the tumor and patients requiring palliative radiation may continue receiving study drug administration if they meet the requirements described in Section 11.1.4. However, for patients who have not had disease progression, the requirement for palliative radiation therapy or surgery will be regarded as disease progression.

Caution should be exercised when administering etoposide phosphate with drugs that are known to inhibit phosphatase activities (eg, levamisole hydrochloride). Although carboplatin has limited nephrotoxic potential, caution should be exercised when administering carboplatin with aminoglycosides, which has resulted in increased renal and/or audiologic toxicity. Any medication that is contraindicated when using etoposide or carboplatin is not permitted, and special warnings and precautions for use of carboplatin and etoposide should be observed.

Necessary supportive care such as antiemetics, antidiarrheals, etc., per the standard of care at the study center will be permitted. **Administration of hematopoietic growth factors in Induction Cycle 1 will not be permitted (ie, no growth factors should be used prior to the actual Induction Cycle 2 Day 1 dosing visit; Section 8.4.5.2).** However, hematopoietic growth factors may be utilized in subsequent cycles at the investigator's discretion as stated in Section 8.4.5.2. To reduce potential immune system interactions, the use of dexamethasone as an antiemetic should be minimized where possible.

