5.1.2.2. Occurrence of GCSF Administrations

Administration of GCSF is collected throughout the induction treatment period. Those cycles where GCSF is administered concurrently will be identified by comparing the start and stop dates of each administration of GCSF to the start of cycle and end of cycle. If any of the dates of administration of GCSF overlap with any dates between the start of cycle and end of cycle, that cycle will be considered as having GCSF administered. Data handling conventions for missing start and stop dates are described in [Section 6.2.5](#).

For the induction treatment period, the total number GCSF administrations is the number of induction cycles in which there is at least one GCSF dose administered. If a patient did not have any GCSF use, the value of 0 will be assigned to that patient. The number of induction cycles where GCSF was NOT given is calculated as total number of induction cycles received – total number of induction cycles where GCSF was administered.

Therefore, any occurrence of a GCSF administration during an induction cycle or the induction treatment period is defined as a binary variable (Yes or No); Yes if total number of induction cycles with GCSF administration ≥ 1 is observed, No for other scenarios.

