The tipping-point analysis assumes all possible combinations of numbers of Yes and No for the missing responses (defined as patients without an event who have less than 4 induction cycles) in the trilaciclib and placebo groups. For example, let n_t be the number of randomized trilaciclib patients with missing response and n_c be the number of randomized placebo patients with missing responses. For the trilaciclib patients with missing values, there are $n_t + 1$ possible assumptions for number of No (i.e. 0, 1, 2, ..., to n_t); for the placebo patients with missing values, there are $n_c + 1$ possible assumptions for number of No. Therefore, there are total of $(n_t + 1) \times (n_c + 1)$ possible combination of assumptions for number of No and Yes for the trilaciclib and placebo patients with missing responses. The un-stratified exact CMH method will be performed on the available responses with each of these $(n_t + 1) \times (n_c + 1)$ assumptions and will be summarized. A figure will be presented with points representing each possible combination where the significant p-value 'tips' to greater than a one-sided 0.025, which would represent a change in the study conclusions. Clinical justification will be provided to evaluate whether the assumption is plausible.

A waterfall plot showing the number of induction cycles with SVN will be presented.

DSN for each induction cycle will be presented using descriptive statistics. The primary analysis on DSN defined by Strategy 1 (refer to [Section 6.2.7.1.1](#)) will be repeated on DSN defined by Strategy 3 (refer to [Section 5.1.1.2.3](#)).

Each of the analyses will be repeated using two additional distinct data sets to evaluate the confounding effect of GCSF administration: inclusion of only those patients or cycles who had concurrent GCSF administration; and inclusion of only those patients or cycles who did NOT have concurrent GCSF administration. The "with" and "without" GCSF analyses are subsets of the total number of patients or cycles.

DSN, Strategy 2 (refer to [Section 5.1.1.2.2](#)) endpoint will be summarized using Kaplan-Meier method, and the descriptive statistics of median, 25% and 75% percentiles along with their 95% CIs will be calculated. Additionally, DSN for each cycle will be presented using descriptive statistics.

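### Splitting the robustness analyses by G-CSF use conditions on a post-randomisation variable that treatment is expected to change, so the subset contrasts cannot show whether G-CSF confounds the effect

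*SAP*

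**What the plan says.** SAP 6.2.7.1.5 plans the repeat, and its aim, in these words: "Each of the analyses will be repeated using two additional distinct data sets to evaluate the confounding effect of GCSF administration". One data set is restricted to G-CSF users, or to the cycles in which it was given. The other is its complement: "inclusion of only those patients or cycles who did NOT have concurrent GCSF administration". The main analyses (SAP 6.2.7.1.1) report p-values for both primary endpoints, an adjusted ratio for occurrence of severe neutropenia (SVN), and differences for its duration in Cycle 1 (DSN). Repeating them implies the same output in each subset. The section gives no caveat on interpretation, and it does not say whether patients or cycles are the unit for a given endpoint.

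G-CSF status comes from dates during induction. If administration overlaps a cycle, "that cycle will be considered as having GCSF administered" (SAP 5.1.2.2). Under Protocol Table 8-3, a first episode of prolonged Grade 4 neutropenia, or of febrile Grade 3/4 neutropenia, leads to "No change. Use G-CSF with subsequent cycles". Table 8-2 gives the same instruction for a low ANC on Day 1 of a cycle. Protocol 8.6 also allows investigator discretion after Cycle 1. For Cycle 1 it says "Administration of hematopoietic growth factors in Induction Cycle 1 will not be permitted", although Protocol 8.4.5.2 has an exception for high-risk fever with neutropenia. G-CSF use is itself a tested endpoint, hypothesis H5 in SAP 6.2.7.1.4. In the earlier first-line study its use "was also significantly lower in the trilaciclib group" (Protocol 4.3.1).

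**The concern.** A confounder of a randomised comparison would have to precede treatment. G-CSF follows randomisation, depends on neutropenia, and is something trilaciclib is meant to reduce. Selecting on it picks different kinds of patient in the two arms. A placebo patient who never needed G-CSF is likely to be at lower risk than the average placebo patient. A trilaciclib patient who did need it is likely to be at higher risk than the average trilaciclib patient. The contrast within a subset then mixes the drug effect with that selection.

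The stake is interpretation. A ratio near 1 in the 'with' set could be read as evidence against the drug, and a very low ratio in the 'without' set as extra support. Both readings would appear in a section on robustness, and neither would be valid.

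**Working it through.** **The documents' own figures.** Protocol 4.3.1 gives G-CSF in 4/38 = 10.5% on trilaciclib and 24/37 = 64.9% on placebo; both percentages reproduce. Grade 4 ANC occurred in 2/38 = 5.3% and 16/37 = 43.2%. At least 24 − 16 = 8 placebo patients therefore received G-CSF without a Grade 4 ANC, so Grade 4 neutropenia is not the only route.

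**Subset sizes if those G-CSF rates recur.** The adjusted sample size is 106 (SAP 2.3), so 53 per arm.
- 'With': 53 × 24/37 = 34.4 placebo; 53 × 4/38 = 5.6 trilaciclib.
- 'Without': 53 × 13/37 = 18.6 placebo; 53 × 34/38 = 47.4 trilaciclib.

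The 1:1 balance is lost in both subsets.

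**Can the split mislead when G-CSF does nothing?** Take the design rates of Grade 4 neutropenia from SAP 2.3: p = 0.45 on placebo and 0.11 on trilaciclib, a true ratio of 0.11/0.45 = 0.24. Assume that G-CSF has no effect on the outcome. Assume also that it is given with probability a to patients with Grade 4 neutropenia and b to the others, by the same rule in both arms. The documents give neither value, so a was varied from 0.6 to 1.0 and b from 0 to 0.4. For a patient-level split:
- G-CSF use: g = p·a + (1 − p)·b
- event rate 'with': p·a / g
- event rate 'without': p·(1 − a) / (1 − g)

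Worked case, a = 0.8 and b = 0.2:
- Placebo: g = 0.36 + 0.11 = 0.47; 'with' 0.36/0.47 = 0.77; 'without' 0.09/0.53 = 0.17.
- Trilaciclib: g = 0.088 + 0.178 = 0.266; 'with' 0.088/0.266 = 0.33; 'without' 0.022/0.734 = 0.03.
- Ratios: 'with' 0.43, 'without' 0.18.

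| a | b | G-CSF use, placebo / trilaciclib | 'with' ratio | 'without' ratio |
|---|---|---|---|---|
| 0.6 | 0.4 | 0.49 / 0.42 | 0.28 | 0.22 |
| 0.8 | 0.2 | 0.47 / 0.27 | 0.43 | 0.18 |
| 0.8 | 0 | 0.36 / 0.09 | 1.00 | 0.17 |
| 0.9 | 0 | 0.41 / 0.10 | 1.00 | 0.16 |
| 1.0 | 0.1 | 0.51 / 0.20 | 0.62 | no events |

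Over the whole grid the 'with' ratio runs from 0.28 to 1.00 and the 'without' ratio from 0.16 to 0.22, against 0.24. The subsets appear to show different effects by G-CSF use although G-CSF is inert.

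**Limits of this illustration.**
- It is not calibrated to the earlier study and should not be combined with the subset sizes above. Fitting one common rule to that study requires 16a + 21b = 24 and 2a + 36b = 4, which gives a = 1.46, an impossible probability.
- The range is not a bound. Suppose b differs by arm so that G-CSF use matches 64.9% and 10.5%, with a = 0.8. The 'with' ratio is then (0.088/0.105)/(0.36/0.649) = 0.836/0.555 = 1.51.
- A separate frailty simulation, with assumed parameters and with Cycle 1 neutropenia driving later G-CSF, gave subset ratios of 0.24 and 0.25 against 0.24 overall. The arms within subsets still differed in mean frailty (0.46 placebo versus 0.28 trilaciclib 'with'; −0.16 versus −0.04 'without').
- With no treatment effect and one common rule, p is equal in both arms and the subset ratio is 1.

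**Endpoint by endpoint.**
- *Cycle 1 DSN, split by cycle:* G-CSF is barred apart from the febrile exception, so 'with' is nearly empty and 'without' is nearly the whole ITT set. The split is uninformative rather than biased.
- *Cycle 1 DSN, split by patient:* G-CSF in later cycles can be triggered by prolonged Grade 4 neutropenia in Cycle 1, so the split selects on the outcome itself.
- *SVN over induction:* the patient-level calculation above applies.
- *G-CSF occurrence (H5):* if it is among the repeated analyses, a patient-level split gives all Yes or all No.

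**The case against.** The strongest reply is that these analyses carry no decision. Efficacy conclusions rest on the multiplicity-adjusted p-values from the ITT analyses (SAP 6.2.7), and no rule uses the subset results. That stands, and it limits the consequence.

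Three further points also stand in part.
- G-CSF is not simply a consequence of the outcome. Day 1 ANC non-recovery and investigator discretion also lead to it. Protocol-directed use starts no earlier than Day 4 of the following cycle, so in a cycle-level split it generally reflects an earlier cycle's neutropenia. It remains post-randomisation and treatment-dependent.
- The scope of the repeat is ambiguous. The sentence follows text on SVN and DSN, and the parallel text in SAP 6.2.7.2.4 confines the split to ANC. The degenerate H5 split arises only on a literal reading.
- The distortion may be small, as the frailty simulation shows.

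A reader might also infer that the plan handles G-CSF in no other way. The documents do not support that. The ITT analysis counts patients regardless of G-CSF, Cycle 1 DSN is tested first in a window where G-CSF is largely barred, and G-CSF use is tested as H5.

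**Conclusion.** The concern holds for what the split can show. Comparisons within G-CSF subsets are not protected by randomisation and cannot answer the question about confounding that the SAP sets them. This follows from the timing of G-CSF, its triggers and its expected difference by arm, and needs no simulation.

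Its size is not established. The ranges in the working rest on inert G-CSF, the design rates, a patient-level split and assumed values of a and b, and another set of assumptions gave little distortion. It would be tempting to say that the split biases the ratio by a known factor, or that it undermines the primary result. Neither is supported: the documents give no cross-tabulation of G-CSF by neutropenia, and the primary tests, gatekeeping and alpha do not use these subsets. The SAP should be corrected before unblinding, as a matter of how supportive results will be read.

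**What to change.** 1. In SAP 6.2.7.1.5, present the with/without G-CSF tables as descriptive, with no treatment p-value and no reference to confounding. State the unit (patient or cycle) for each endpoint and exclude the G-CSF endpoint. Apply the same label to the split in SAP 6.2.7.2.4.
2. Assess robustness to G-CSF in all ITT patients by randomised arm, using (a) occurrence of SVN in Cycle 1, largely before G-CSF is allowed, and (b) a Yes/No composite of SVN or G-CSF during induction.

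Both variables follow from derivations already in SAP 5.1.1.1 and 5.1.2.2, so the cost is SAP wording and a little programming, with no new data. There are drawbacks. The subset p-values are lost. Analysis (a) overlaps with Cycle 1 DSN, which is zero without SVN. Analysis (b) overlaps with H5 and includes discretionary G-CSF; at the earlier study's placebo rates (64.9% G-CSF against 43.2% Grade 4 ANC) it could be driven largely by G-CSF.

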Diagnosis and Main Criteria for Inclusion	
For a patient to be eligible for participation in this study, all of the following criteria must apply.
 

1. Age <math>\geq</math> 18 years

2. Unequivocally confirmed diagnosis of SCLC by histology or cytology, preferably including the presence of neuroendocrine features by immunohistochemistry

3. Extensive-stage SCLC

4. At least 1 target lesion that is measurable by RECIST v1.1 (Eisenhauer 2009)

5. Hemoglobin <math>\geq</math> 9.0 g/dL

6. ANC <math>\geq</math> <math>1.5 \times 10^9/L</math>

7. Platelet count <math>\geq</math> <math>100 \times 10^9/L</math>

8. Creatinine <math>\leq</math> 1.5 mg/dL or glomerular filtration rate (GFR) of <math>\geq</math> 60 mL/minute

9. Total bilirubin <math>\leq</math> <math>1.5 \times</math> ULN; <math><</math> <math>3 \times</math> ULN if the patient has documented Gilbert's disease

10. Aspartate aminotransferase (AST) and alanine aminotransferase (ALT) <math>\leq</math> <math>2.5 \times</math> ULN; <math>\leq</math> <math>5 \times</math> ULN in the presence of liver metastases

11. ECOG performance status of 0 to 2

12. Predicted life expectancy of <math>\geq</math> 3 months

13. Contraception:

a. For females: All females of childbearing potential must have a negative serum beta human chorionic gonadotropin (<math>\beta</math>-hCG) test result at screening. Females must be either postmenopausal, surgically sterile, or agree to use 2 forms of highly effective contraception during the study and for 6 months following discontinuation of study treatment

i. Postmenopausal is defined as (1) at least 60 years of age, (2) medically confirmed ovarian failure, or (3) younger than 60 years of age and have had cessation of regular menses for at least 12 consecutive months with no

---

---

alternative pathological or physiological cause, and/or serum levels of estradiol and follicle stimulating hormone within the laboratory's reference range for postmenopausal females

- ii. Acceptable surgical sterilization techniques are complete or partial hysterectomy, bilateral tubal ligation with surgery at least 6 months prior to dosing, or bilateral oophorectomy with surgery at least 2 months prior to dosing

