5. PRIMARY AND SECONDARY ENDPOINTS

The following general definitions will be applied to all endpoints derivation unless otherwise specified.

Term	Definition
Severe Neutropenia (SVN)	ANC lab value that meets the common terminology criteria for adverse events (CTCAE) criteria for \geq Grade 4 toxicity
Cycle baseline	The last non-missing value within the window starting from 3 days prior to the date/time of study drug administration on Day 1 of Cycle 1 and 1 day prior to Day 1 of each subsequent cycle (i.e. Cycle 2, Cycle 3, etc.); must be prior to the time of study drug administration
Cycle nadir	The lowest value for a given hematologic parameter that occurs between start of cycle and end of cycle and is less than the cycle baseline.
Duration of cycle	Total number of days from start of cycle to end of cycle, that is, date of end of a cycle - date of start of cycle + 1.
End of cycle*	Day 1 of the subsequent cycle. For example, the end of cycle for Cycle 1 is Day 1 of Cycle 2. For the last induction cycle (where no subsequent maintenance cycle is given), the end of cycle will be defined as Day 36 after the first dose of the cycle. For the last maintenance cycle, the end of cycle will be defined as Day 30 after the first dose of the cycle.
Start of cycle	Day 1 of each cycle starts with the administration of study drug(s) (etoposide, carboplatin, atezolizumab, or trilaciclib)
Start of study	Date of randomization
Study baseline	The last non-missing value prior to, or on the date of administration of study drug(s) (etoposide, carboplatin, atezolizumab, or trilaciclib); must be prior to the time of study drug administration
Change from baseline	Calculated as the post-baseline value minus the baseline value. If the baseline value is missing for a particular endpoint, change from baseline will be missing.
Induction treatment period	Between the date of randomization and end of cycle for the last Induction cycle.
Maintenance treatment period	Between the date of Day 1 of the first maintenance cycle and end of cycle for the last Maintenance cycle.
Overall treatment period	Between the date of randomization and end of cycle for the last cycle.

* For various hematologic parameter analyses, the last assessment prior to end of cycle will be utilized in the analyses. Situations where this applies will be indicated as such.

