6.2.2. Demographic and Other Baseline Characteristics

Demographic and other baseline characteristics, such as age at informed consent date, age groups (18-65, >65-75, >75), gender, race, ethnicity, country, screening vital signs (body weight, height, BMI, BSA), ECOG status, presence of brain metastases, and smoking history (never smoker, former smoker and current smoker), will be summarized and listed.

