6.2.7.1.2 Key Secondary Efficacy Analyses

Occurrence of RBC transfusions on/after 5 weeks on study is a binary variable and will be summarized using the same method for occurrence of SVN described in [Section 6.2.7.1.1](#) except baseline HGB will be used as a covariate instead of baseline ANC in the modified Poisson model. Also, the offset will be the logarithm transformation of duration of induction treatment period divided by 7 (i.e. week) instead of number of induction cycles, and. An additional sensitivity analysis will look all transfusions during the induction treatment period, and all transfusions with a subset of subjects completing at least 1 cycle.

Occurrence of GCSF administration is a binary variable and will be summarized using the same method for occurrence of SVN described in [Section 6.2.7.1.1](#).

All-cause dose reductions will be analyzed to compare trilaciclib and placebo using a negative binomial regression model to account for the potential over-dispersion. The model includes the stratification factors of ECOG (0 or 1 vs. 2) and brain metastases (Yes vs. No), and treatment as a fixed effect. The logarithm transformation of number of induction cycles will be included as an offset variable in the modeling. The two-sided p-value, aRR (trilaciclib vs placebo) and its 95% CIs will be presented.

The total number of all-cause dose reductions will be summarized descriptively, along with the number of induction cycles, and the event rate per cycle (calculated as the total number of events/total number of induction cycles). The cumulative incidence of events during the induction treatment period will be summarized and presented graphically by cycle.

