In addition to the summary from Kaplan-Meier method, the two-sided p-value will be obtained from the stratified Kaplan-Meier method to account for the stratification factors. The hazard ratio (HR) between the two treatments (trilaciclib vs placebo), together with its 95% CIs will be calculated from a Cox proportional hazard model in which treatment and the stratification factors will be included as fixed effects.

For the time (days) to first occurrence of a MAHE event, a graphical display of cumulative incidence will be presented.

The primary and key secondary efficacy endpoints are based on the ITT analysis set, and the analysis will be repeated for the mITT analysis set and PP analysis set.

For RBC transfusions, subsets of subjects with baseline HGB <9 g/L and ≥ 9 g/L will be provided, as well as a summary of the number of units transfused.

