6.2.9. Subgroup Analyses

The MAHE will be examined in the following subgroups:

- Age group (ages <65; >65).
- Gender (Male; Female).
- Brain metastases (Yes; No).
- ECOG performance status (0-1; 2).
- Race (Caucasian; non-Caucasian).
- Region (US; Ex-US).
- Baseline LDH (\leq ULN; $>$ ULN).

Descriptive statistics by treatment group will be presented for each subgroup of patients. Additional subgroups or endpoints may be identified and explored.

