AST	>ULN – 3.0 x ULN	>3.0 – 5.0 x ULN	>5.0 – 20.0 x ULN	>20.0 x ULN	-
Bilirubin	>ULN – 1.5 x ULN	>1.5 – 3.0 x ULN	>3.0 – 10.0 x ULN	>10.0 x ULN	-
Calcium (Hypercalcemia)	Corrected serum calcium of >ULN – 11.5 mg/dL; >ULN – 2.9 mmol/L; Ionized calcium >ULN - 1.5 mmol/L	Corrected serum calcium of >11.5 – 12.5 mg/dL; >2.9 – 3.1 mmol/L; Ionized calcium >1.5 - 1.6 mmol/L	Corrected serum calcium of >12.5 – 13.5 mg/dL; >3.1 – 3.4 mmol/L; Ionized calcium >1.6 - 1.8 mmol/L	Corrected serum calcium of >13.5 mg/dL; >3.4 mmol/L; Ionized calcium >1.8 mmol/L	-
Calcium (Hypocalcemia)	Corrected serum calcium of <LLN – 8.0 mg/dL; <LLN – 2.0 mmol/L; Ionized calcium <LLN - 1.0 mmol/L	Corrected serum calcium of <8.0 – 7.0 mg/dL; <2.0 – 1.75 mmol/L; Ionized calcium <1.0 - 0.9 mmol/L	Corrected serum calcium of <7.0 – 6.0 mg/dL; <1.75 – 1.5 mmol/L; Ionized calcium <0.9 - 0.8 mmol/L	Corrected serum calcium of <6.0 mg/dL; <1.5 mmol/L; Ionized calcium <0.8 mmol/L	-
CK	>ULN – 2.5 x ULN	>2.5 x ULN – 5 x ULN	>5 x ULN – 10 x ULN	>10 x ULN	-
Creatinine	>1 – 1.5 x baseline; >ULN – 1.5 x ULN	>1.5 – 3.0 x baseline; >1.5 – 3.0 x ULN	>3.0 x baseline; >3.0 – 6.0 x ULN	>6.0 x ULN	-
GGT	>ULN – 2.5 x ULN	>2.5 – 5.0 x ULN	>5.0 – 20.0 x ULN	>20.0 x ULN	-
Glucose (Hyperglycemia)	Fasting glucose value >ULN – 160 mg/dL; Fasting glucose value >ULN – 8.9 mmol/L	Fasting glucose value >160 – 250 mg/dL; Fasting glucose value >8.9 – 13.9 mmol/L	Fasting glucose value >250 – 500 mg/dL; Fasting glucose value >13.9 – 27.8 mmol/L	Fasting glucose value >500 mg/dL; Fasting glucose value >27.8 mmol/L	-
Glucose (Hypoglycemia)	<LLN – 55 mg/dL; <LLN – 3.0 mmol/L	<55 – 40 mg/dL; <3.0 – 2.2 mmol/L	<40 – 30 mg/dL; <2.2 – 1.7 mmol/L mmol/L	<30 mg/dL; <1.7 mmol/L	-

Parameter	Grade				
	1	2	3	4	5
Hemoglobin	<LLN – 10.0 g/dL; <LLN – 6.2 mmol/L; <LLN – 100 g/L	<10.0 – 8.0 g/dL; <6.2 – 4.9 mmol/L; <100 – 80 g/L	<8.0 g/dL; <4.9 mmol/L; <80 g/L	-	-
Lipase increased	>ULN - 1.5 x ULN	>1.5 - 2.0 x ULN	>2.0 - 5.0 x ULN	>5.0 x ULN	-
Potassium (Hyperkalemia)	>ULN – 5.5 mmol/L	>5.5 – 6.0 mmol/L	>6.0 – 7.0 mmol/L	>7.0 mmol/L	-
Potassium (Hypokalemia)	<LLN – 3.0 mmol/L	-	<3.0 – 2.5 mmol/L	<2.5 mmol/L	-
Lymphocyte	<LLN – 800/mm ³ ; <LLN – 0.8 x 10 ⁹ /L	<800 – 500/mm ³ ; <0.8 – 0.5 x 10 ⁹ /L	<500 – 200/mm ³ ; <0.5 – 0.2 x 10 ⁹ /L	<200/mm ³ ; <0.2 x 10 ⁹ /L	-
ANC	<LLN – 1500/mm ³ ; <LLN – 1.5 x 10 ⁹ /L	<1500 – 1000/mm ³ ; <1.5 – 1.0 x 10 ⁹ /L	<1000 – 500/mm ³ ; <1.0 – 0.5 x 10 ⁹ /L	<500/mm ³ ; <0.5 x 10 ⁹ /L	-

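### Two descriptive subsets in the SAP need repair: the baseline hemoglobin split for RBC transfusions is empty below its cut as written (and near empty once the unit is corrected), and the MAHE age groups have no place for age 65.

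*SAP*

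**What the plan says.** **Hemoglobin.** SAP Section 6.2.7.1.5, on robustness of the primary and key secondary analyses, plans the following: "For RBC transfusions, subsets of subjects with baseline HGB <9 g/L", with a complementary group at or above the same value. Occurrence of RBC transfusion on or after Week 5 is a key secondary endpoint and is H4 in SAP Section 6.2.7.1.4. Its main model, in SAP Section 6.2.7.1.2, follows the model for severe neutropenia "except baseline HGB will be used as a covariate instead of baseline ANC in the modified Poisson model".

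Protocol Section 7.1.1, criterion 5, requires hemoglobin of at least 9.0 g/dL at entry. Protocol Section 10.3.1 has hematology reviewed before the first dose and lets only patients who still meet every criterion start Induction Cycle 1. SAP Section 5 defines study baseline as the last non-missing value before study drug.

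**Age.** SAP Section 6.2.9 lists the age subgroups for MAHE as "Age group (ages <65; >65". SAP Section 6.2.2 uses different bands for the baseline table: "age groups (18-65, >65-75, >75". In that table age 65 belongs to the lowest band.

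**The concern.** A subset rule should put every patient in exactly one group, and each group should hold enough patients to be worth reading. Neither rule meets this standard.

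The hemoglobin rule uses a unit that puts everyone above the cut. The obvious correction moves the cut onto the entry limit, so a programmer who silently changes g/L to g/dL still produces one column that repeats the overall result and one with almost nobody in it. SAP Section 6.2.9 lists no baseline hemoglobin subgroup, so this is the only named subset by that variable.

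The age rule uses two strict inequalities and leaves a gap at the cut point. Patients in the gap would drop out of the age table without notice.

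What is at stake is the usefulness and completeness of two descriptive displays. There is also a procedural cost: if the cuts are repaired after unblinding, prespecified subsets become post hoc choices.

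**Working it through.** The plan states no expected size for either subset, so there is no figure of its own to reproduce. The checks are a unit conversion, a comparison with the entry rule, and a test of whether the categories cover all ages.

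**1. Unit.** The hemoglobin row of the SAP's CTCAE grading table (Table A-1) gives Grade 3 as "<8.0 g/dL; <4.9 mmol/L; <80 g/L". It also pairs 10.0 g/dL with 100 g/L.
- Conversion factor: 80 / 8.0 = 10 and 100 / 10.0 = 10, so g/L = 10 × g/dL.
- Planned cut: 9 g/L = 9 / 10 = 0.9 g/dL.
- Entry limit: 9.0 g/dL = 90 g/L.
- Ratio of planned cut to entry limit: 9 / 90 = 0.1.

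As written, the lower subset is expected to hold 0 patients, and the upper subset is the whole population.

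**2. The cut read as 9 g/dL.** At screening, every eligible patient is at or above 9.0 g/dL, so the lower subset is empty by design. At baseline, a value below 9.0 could come from three sources:
- an eligibility deviation;
- a patient randomized but not dosed, who remains in the ITT set (SAP Section 3.1.1);
- an isolated fall between screening, up to 14 days before dosing (Protocol Section 10.1), and the last pre-dose value.

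Protocol Section 10.3.1 limits the third source, because the criteria must still hold on Day 1. The documents give no hemoglobin distribution, so the number cannot be calculated. The rules support near empty, and they do not support exactly empty.

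**3. Age coverage.** With age in completed years, the groups are 64 and under, and 66 and over. Age 65 is in neither.

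**4. Size of the age gap (assumed distributions).**
- Normal age with mean μ and SD σ: share aged 65 = Φ((66 − μ)/σ) − Φ((65 − μ)/σ), evaluated for means of 60, 64 and 68 and SDs of 7, 9 and 11.
- Smallest share: μ = 60, σ = 11, giving 0.0320.
- Largest share: μ = 64, σ = 7, giving 0.0557.
- Of 100 patients: 3.2 to 5.6. Of 106 patients: 3.4 to 5.9.
- Uniform over ages 50 to 80 (31 ages): 1/31 = 3.2%, and 106 × 0.032 = 3.4.

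The range is about 3 to 6 patients. The totals of 100 and 106 are the approximate enrollment and the adjusted sample size in Protocol Section 13.1 and SAP Section 2.3.

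**The case against.** **The unit is a misprint that nobody would run.** Every hemoglobin limit in the protocol is in g/dL, and a competent programmer would not code 0.9 g/dL. That is fair, and it makes the unit alone an editorial matter. It does not rescue the split, because the corrected cut coincides with the entry limit.

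**A cut at 9 g/dL may be deliberate.** The split sits under robustness, and the upper group would show the result without patients below the entry limit. This is a possible purpose, and the SAP states none. A reader might infer that the split was meant to test whether the transfusion effect holds across baseline anemia, and that this test has been lost. The SAP never says so. The fix below is therefore conditional on the purpose.

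**The transfusion result does not depend on the subset.** This stands. Baseline hemoglobin is already a covariate in the model for H4. A covariate does not examine effect modification, but SAP Section 6.2.9 leaves room for further exploratory subgroups. A reader who concluded that H4 is weakened would go beyond the documents.

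**Age may not be in whole years.** SAP Section 6.2.2 refers to age at the consent date without a formula, and SAP Section 6.1.1 presents derived variables to one decimal place. With decimal age, hardly anyone would be exactly 65. Integer cut points make completed years the likelier reading, but the loss is conditional on it.

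**The two age groupings need not agree.** This is also right. A three-band baseline table and a two-band subgroup may differ. The defect is the gap in Section 6.2.9; the mismatch by itself is not an error.

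**Conclusion.** Both rules are wrong as written, and the consequence is minor.

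- **Hemoglobin.** The lower subset is empty at 9 g/L. It is near empty at 9 g/dL, given the entry criterion and its re-check on Day 1. The first statement follows from the documents' own figures. The second rests on the eligibility rules being followed.
- **Age.** If age is in completed years, patients aged 65 are left out of the MAHE age subgroups: about 3 to 6 of 100 to 106 under the assumed distributions. With decimal age the loss is close to nil.

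Both are descriptive, supportive displays outside the multiplicity procedure, and MAHE is itself a supportive endpoint in this SAP (Section 5.1.3.1). Type I error, power, and the primary and key secondary tests are unaffected.

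**What to change.** Before unblinding, amend two places in the SAP.

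1. **Section 6.2.7.1.5.** State the hemoglobin cut in g/dL and say what the subset is for. If the aim is to set aside patients below the entry limit, 9 g/dL can stay, with a note that the lower group will be very small. If the aim is to show consistency across baseline hemoglobin, use a cut above 9.0 g/dL that divides eligible patients. The documents contain nothing to show how any fixed value would divide them, so the pooled blinded median is the safer choice.
2. **Section 6.2.9.** Make the age groups exhaustive: <65 and ≥65, or ≤65 and >65 if they are to match the baseline table. State that age is in completed years at consent, if that is so.

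The cost is a few lines of SAP text. No visit, data item or sample size changes. The one drawback is that a median cut depends on the data and replaces the planned value, so it should be computed on blinded pooled data and documented.
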